### **15.4. Sample**

Adults over the age of 18 who attend SARCs and who consent to participate within the recruitment period (or until sample size is reached).

The Inclusion Criteria are as follows:

- 1.) Aged 18 or older
- 2.) Can read and understand English (or there are suitable confidential translation services available)

The Exclusion Criteria are as follows:

- 1.) Lack of capacity to provide informed consent.
- 2.) Where participation is deemed to significantly increase risk to self or others.
- 3.) Attendee of a SARC not participating in the study

To meet power requirements, a total sample size of n=360 across the six sites should be obtained (n=60 at each site). With an estimated population of 4000 across 6 sites per year, we estimate attendees at each SARC will be 40-60 referrals per site, per month. In a recent 12-month audit of mental health needs in Thames Valley SARCs (Brooker et al., under review) the SARC staff obtained

consent and collected data on 42% of attendees and 38% declined to participate (with limited support to recruit). Therefore we are confident that we should be able to obtain consent from 50% of attendees to participate which means 20-30 per site, per month. If we assume 20 per month (~50%) consent to participate x 6 sites= 120; therefore, sample size would be reached in 3 months; 120 x 3 =360, with 3 months leeway for variation. Extra sites may be added as necessary.

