### **15.9. Health Economics**

Little is known about what services SARC attendees use and the related costs. The aims of the health economics analysis in WP3 will be to:

- (i) Provide descriptive statistics of resource use and costs for adult SARC attendees at recruitment and 6 months;
- (ii) Calculate quality adjusted life years (QALYs) over 6 months;
- (iii) Calculate the predictors of costs and QALYs; and
- (iv) Quantify the relationship between costs and QALYs using general linear models.

Resource use will be costed using nationally published sources. In addition to reporting descriptive statistics of service use and costs we will use general linear models using appropriate family and link functions to provide descriptive statistics of predicted costs for different patient characteristics. In particular, we will evaluate the relationship between patient care pathway, costs and quality of life outcomes such as CORE and ReQoL to identify if engagement with services is predictive of better or worse quality of life. QALYs will be calculated from the ReQoL using algorithms currently under development by The University of Sheffield to calculate the area under the curve. We will use the AIC to decide the model structure which variables to include in the models (Barber and Thompson, 2004). For people missing data at 6 months we will evaluate baseline predictors of missing data and use these to construct multiple imputed datasets using chained equations. Final analyses will be conducted on the imputed data datasets.

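### Section 15.9 lets AIC decide which variables enter models meant to identify predictors, so it can list irrelevant ones, inflate weak effects and drop the engagement term it asks about

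*Protocol*

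**What the plan says.** Protocol section 15.9 (Health Economics, WP3) gives the models two kinds of job.

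- **Descriptive or predictive:** "we will use general linear models using appropriate family and link functions to provide descriptive statistics of predicted costs for different patient characteristics".
- **Identifying predictors:** aim (iii) is "Calculate the predictors of costs and QALYs". The section also wants the link between care pathway, costs and outcomes such as CORE and ReQoL examined, "to identify if engagement with services is predictive of better or worse quality of life".

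One rule governs what enters the models: "We will use the AIC to decide the model structure which variables to include in the models". The section gives no candidate list, names no variable that must stay in, and describes no validation or correction after selection.

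For people without 6-month data, baseline predictors of missingness are to be found and the team will "use these to construct multiple imputed datasets using chained equations". Then: "Final analyses will be conducted on the imputed data datasets". The section does not say how AIC selection and the imputed datasets are to be combined.

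**The concern.** AIC trades fit against the number of parameters. It is a reasonable tool for choosing a family and link, or for building a model whose only purpose is to predict costs. It is poorly matched to deciding which variables are predictors, because the selection step then supplies part of the answer. Three things follow.

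1. Irrelevant variables are retained far more often than 5% of the time.
2. Weak effects that survive are overstated, and their standard intervals take no account of the search.
3. A variable of direct interest can be removed. If engagement is treated like any other candidate and AIC drops it, the section's own question ends with no estimate and no interval.

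This is a method that the protocol itself fixes, not a detail left open, so an SAP consistent with the protocol would inherit it.

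**Working it through.** The protocol states no error rate for this step, so there is no figure to reproduce.

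**Inputs.** From the protocol: the AIC rule, the aims and the use of imputed datasets (15.9), and the target sample, "a total sample size of n=360 across the six sites should be obtained (n=60 at each site" (15.4). By definition, AIC charges 2 per parameter; the protocol states no other penalty. Assumed, because the protocol gives no figure: number of candidates, share missing at 6 months, number of imputations, and backward selection.

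**1. Retention of an irrelevant variable.** AIC keeps a term with d parameters when its likelihood-ratio statistic exceeds 2d. For a null term the chance is P(χ²_d > 2d).

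| d | Chance kept |
|---|---|
| 1 | 15.7% |
| 2 | 13.5% |
| 3 | 11.2% |
| 5 (e.g. six sites) | 7.5% |

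Simulation at n = 180 to 360 agrees for d = 1: 15.7–17.3% (gamma, log link) and 15.1–16.9% (Gaussian).

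For k independent null one-parameter candidates, the expected number kept is 0.157k and the chance of at least one is 1 − (1 − 0.157)^k. With k = 10: 1.6 and 82%. With k = 20: 3.1 and 97%. These count retained variables, not significant ones.

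**2. False positives if intervals are read.** A null term kept at |z| > √2 has a 95% interval covering zero with probability (0.157 − 0.05)/0.157 = 68%. The chance of being both kept and apparently significant is 0.157 × 0.32 = 5.0%. Searching over many terms raises this slightly. With n = 360, 15 independent null candidates, a Gaussian outcome, backward AIC and 2,000 runs:

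- AIC kept 2.48 nulls per model, of which 0.81 had a 95% CI excluding zero: 0.81/15 = 5.4% per null variable.
- The full model gave 0.76/15 = 5.1%.
- With correlated covariates the rate after selection was 6.5–7.5%, against about 5% for the full model. It depends on how strong the correlation is.

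**3. Overstatement of weak effects.** Let Z be normal with mean μ = δ√360 and variance 1, with δ the true standardised effect and P the probability that |Z| > √2. The average estimate when kept, relative to the truth, is 1 + [φ(√2 − μ) − φ(√2 + μ)]/(μP).

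- δ = 0.05: μ = 0.949, P = 0.330, ratio 1 + 0.333/0.313 = 2.07 (simulated 2.0).
- δ = 0.10: μ = 1.897, P = 0.686, ratio 1 + 0.353/1.302 = 1.27 (simulated 1.26).

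**4. Losing the engagement term.** For a one-parameter term treated as an ordinary candidate, the chance of being dropped is 1 − P. That is 84% if it has no effect and 31% if δ = 0.10. Simulation gave about 83% and 35%.

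**5. AIC with imputed data.** Assume 10 candidates (one real), 20 imputations, n = 360, AIC rerun in each imputed dataset, and 60 runs per setting.

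| Missing | Mean distinct models among 20 | Runs in which all 20 agreed | A null kept within one imputed dataset |
|---|---|---|---|
| 20% | 9.4 | 0 | 26% |
| 30% | 13.2 | 0 | 31% |
| 50% | 17.4 | 0 | 43% |

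This shows what happens without a combining rule. It does not show that the team would proceed this way.

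**The case against.** **The harm depends on how results are read.** A reader might infer that about 16% of irrelevant variables would be reported as findings. The protocol does not say that retention alone makes a variable a predictor, and it sets no significance level here. If every retained term is printed with its interval, about two thirds of the retained nulls would visibly include zero, and the excess over 5% is small. This stands. The 16% is a false-listing rate only if the retained variables are themselves the reported predictors, which aim (iii) permits but does not state.

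**The models are partly descriptive.** Predicted costs by patient characteristic are a stated purpose, the AIC sentence cites a methods paper on regression of cost data, and AIC is acceptable for prediction. This also stands, but it does not cover aim (iii) or the engagement question.

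**Engagement may be fitted by design.** The section singles out care pathway for evaluation, which could mean that it is always in the model. If so, the drop rates above do not apply to it. The text does not say so, and the AIC sentence carries no exception. The supportable statement is that AIC may drop the term, not that it will.

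**Imputation.** A reader might infer that AIC and multiple imputation cannot yield one model. That is too strong. Only the final analyses are placed on the imputed data. One model could be chosen on complete cases, by averaged or stacked AIC, by majority vote or by pooled tests, and an SAP could name any of these.

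**Conclusion.** The point holds as a mismatch between a stated selection rule and a stated aim. Using AIC to choose variables gives a retention rate of 15.7% per irrelevant one-parameter term and 11.2% for 3 df. Read through unadjusted 95% intervals, the false-positive rate is about 5.4% with independent covariates and about 7% with correlated ones.

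The more serious consequences are overstated weak effects (about 2-fold at a standardised effect of 0.05 and 1.3-fold at 0.10, n = 360), intervals that ignore the selection, and possible loss of the engagement estimate: more than 80% of the time if its effect is null and about a third of the time at 0.10, if AIC is free to drop it.

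The retention rates rest only on the definition of AIC and large-sample theory. The other figures assume n = 360 with complete data and, where simulated, the candidate sets described. The missing rule for combining AIC with imputation is a secondary gap. Only the health-economic models are affected; the WP3 prevalence estimate in section 15.8 is not. The change is worth making, but it does not threaten the study's main result.

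**What to change.** In section 15.9:

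1. List the candidate predictors for each outcome before the 6-month data are seen, and state that the care-pathway and engagement terms are always retained.
2. Fit that one model per outcome in every imputed dataset, pool by Rubin's rules, and report every estimate with its 95% CI. This also removes the question of how to combine AIC across imputations.
3. Keep AIC for choosing family and link, or for a cost model clearly labelled as prediction only. If a shorter cost model is wanted, bootstrap imputation and selection together and report how often each variable is chosen.

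The cost is wording and a little extra analysis, with no new data. Intervals will be somewhat wider than those from a selected model. The number of terms must suit the observed 6-month sample: 20 terms give 360/20 = 18 people per term with no loss, but 0.70 × 360 = 252 and 252/20 = 12.6 per term if 30% are missing (an assumed figure).

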### **15.1. Aims**

Work Package 3 has the following aims:

- 1.) To estimate the prevalence of mental health and substance use difficulties in cohort of people attending SARCs
- 2.) To assess how the identified mental health and substance misuse needs have been met at a 6month follow-up point
- 3.) To calculate quality adjusted life years (QALYs) over the 6 months

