### **15.8. Analysis**

The demographics of our prevalence study sample, both non-recent and recent cases, will be initially compared to routine data collected from the 6 sites over the course of the national survey (WP2) in order to assess representativeness of our sample. The final dataset will then be weighted for demographics (e.g. age, gender, deprivation).

A direct estimate of the prevalence of mental health within SARC attendees will be determined from the sample and weighted estimates produced for the 6 SARC sites. Additionally, a further weighted national estimate will be produced (if demographic data can be obtained for all 47 SARC sites).

Analysis of other health, wellbeing and behavioral measures will follow the same principle to produce direct (and site-specific and national weighted) estimates. Prior to producing these estimates, the dataset will be analyzed to determine how/if demographics, site or method of data collection have influenced prevalence measures. A logistic multivariate analysis will be undertaken to determine predictors of mental health and/substance use diagnosis. Participant's feedback on satisfaction with services and any gaps/unmet need will also be analyzed descriptively and themed in order to glean qualitative insights.

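### Section 15.9 names only baseline predictors of missingness for the imputation model; followed as written, this shrinks the 6-month association of any analysis covariate that does not also predict drop-out

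*Protocol*

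**What the plan says.** All the relevant text is in protocol section 15.9 (Health Economics, Work Package 3).

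- **How the imputation model is built:** "we will evaluate baseline predictors of missing data and use these to construct multiple imputed datasets using chained equations". No other input is listed.
- **What is run on the result:** "Final analyses will be conducted on the imputed data datasets". No complete-case comparison is mentioned.
- **What those analyses are:** predictors of costs and of QALYs; the cost-QALY relationship ("Quantify the relationship between costs and QALYs using general linear models"); and care pathway against outcome ("we will evaluate the relationship between patient care pathway, costs and quality of life outcomes such as CORE and ReQoL").
- **How analysis covariates are chosen:** "We will use the AIC to decide the model structure which variables to include in the models". The text does not link this choice to the imputation variables.

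The planned sample is 360 (section 15.4). Section 15.7.1 allows up to five contact attempts before a person is recorded as not contactable. No 6-month attrition rate is given.

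**The concern.** Multiple imputation preserves an association only if the variables concerned are in the imputation model. The stated rule selects variables by a different criterion, namely whether they predict being missing. A baseline variable can matter a great deal for cost or quality of life and have nothing to do with drop-out. Under the rule it does not qualify, and missing outcomes are then generated as if unrelated to it.

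This bears directly on the stated aims of section 15.9, which are about associations. Because covariates are chosen separately by AIC, nothing in the text keeps the two sets aligned. A coefficient weakened by the imputation could also cause AIC to drop a real predictor; that last step is reasoning and was not simulated.

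**Working it through.** **Plan's own figures.** The protocol gives no attrition rate, effect size or number of imputations, so there is no figure to reproduce on this point. The sample size used below agrees with section 15.4: 60 × 6 = 360 and 20 × 6 × 3 = 360.

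**Expected shrinkage.** Let *f* be the fraction imputed and *b* the true coefficient of a fully observed covariate *x* that is unrelated to drop-out. Observed rows carry slope *b*. Rows imputed without *x* carry slope 0. The pooled slope is therefore about (1 − *f*) × *b*, which is 0.80*b*, 0.70*b* and 0.60*b* at *f* = 20%, 30% and 40%.

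**Simulation.** Assumed set-up:

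- n = 360, 600 replicates, 5 imputations with parameters redrawn each time.
- *w* and *x* are independent standard normal baseline variables. Cost = 0.3*w* + 0.4*x* + error. QALY = 0.3*w* + 0.4*x* + 0.4 × cost + error, treated as one 6-month variable.
- Cost and QALY are missing together, with probability depending on *w* only.
- Analysis models: cost on *w*, *x*; QALY on *w*, *x*, cost. All three target coefficients are 0.40.

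Imputation models: **A**, *w* only, each outcome imputed separately; **B**, chained, *w* plus the other 6-month outcome, *x* omitted; **C**, as B with *x* included.

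Ratio of estimate to truth (*x* on cost / *x* on QALY / cost on QALY):

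| Missing | A | B | C | Complete cases |
|---|---|---|---|---|
| 20% | 0.79 / 0.86 / 0.84 | 0.79 / 0.76 / 1.14 | 0.99 / 1.01 / 1.00 | 1.00 / 1.01 / 1.00 |
| 30% | 0.70 / 0.78 / 0.75 | 0.70 / 0.66 / 1.19 | 1.01 / 1.02 / 0.99 | 1.00 / 1.02 / 0.99 |
| 40% | 0.60 / 0.68 / 0.65 | 0.60 / 0.54 / 1.22 | 1.00 / 1.00 / 0.99 | 1.00 / 1.00 / 0.99 |
| 50% | 0.50 / 0.58 / 0.57 | 0.50 / 0.45 / 1.28 | 1.00 / 1.00 / 1.01 | 1.00 / 1.00 / 1.01 |

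A simpler one-outcome simulation (400 datasets, 10 imputations, true coefficient 0.40) gave 0.315, 0.274 and 0.237 at about 20%, 30% and 40% missing with *x* omitted, and 0.399, 0.406 and 0.399 with *x* included.

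**Reading the table.**

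1. The coefficient of *x* on cost follows 1 − *f* under both A and B. Letting the 6-month outcomes inform each other does not rescue an omitted baseline covariate.
2. The cost-QALY slope falls under A but rises by 14% to 28% under B. With *x* omitted, cost stands in for it: the slope used for imputation is 0.4 + 0.4 × 0.4 / (0.4² + 1) = 0.4 + 0.16/1.16 = 0.54 instead of 0.40.
3. Complete cases are unbiased here because the variable that drives missingness is also in the analysis model. That need not hold in the real data.

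**QALYs as an area under the curve.** With measurements at 0 and 6 months, QALY = 0.5 × (u0 + u6)/2 = 0.25u0 + 0.25u6. If *x* has effects b0 and b6 on the two utilities and only u6 is imputed, the ratio is 1 − *f* × b6/(b0 + b6). With b0 = b6 (an assumption) this is 0.90, 0.85 and 0.80 at 20%, 30% and 40% missing, half the shrinkage. If the analysis adjusts for baseline ReQoL, this relief goes, because only the 6-month half then bears on the coefficient.

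**The case against.** The strongest reply is that the protocol names one input and excludes nothing. Chained equations ordinarily condition each incomplete variable on the others in the set, so 6-month costs, CORE and ReQoL would normally inform one another. The full variable list is commonly left to a statistical analysis plan, which is not to hand. This stands in part: a reader should not infer that the protocol restricts the imputation model to these variables. But the sentence is more than silence. It gives a criterion for choosing variables, the criterion is the wrong one for association analyses, and the usual behaviour of chained equations does not protect an omitted baseline covariate (model B).

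Three further inferences are tempting and not supported.

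- **That every association is pulled toward zero.** The cost-QALY slope rose in model B, so its direction is not determined.
- **That the percentages apply to all covariates and outcomes.** They are for a fully observed baseline covariate wholly omitted from the imputation. Service use is collected at 6 months and would be missing together with the outcomes, so it would itself be imputed. QALYs use observed baseline data as well.
- **That the 6-month needs aim ("To assess how the identified mental health and substance misuse needs have been met at a 6month follow-up point") is left to responders.** Section 15.8 says "Participant's feedback on satisfaction with services and any gaps/unmet need will also be analyzed descriptively and themed in order to glean qualitative insights". It neither applies nor excludes the imputed datasets, and themed material is not ordinarily imputed. Service use is analysed in section 15.9, where the imputed datasets do apply. At most this calls for a clarification, and it is not part of the finding.

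**Conclusion.** The point holds in conditional form and should be corrected. If the sentence in section 15.9 is followed as written, an analysis covariate that predicts 6-month costs, CORE or ReQoL but not drop-out has its own 6-month coefficient reduced by about 20% to 40% when 20% to 40% of outcomes are imputed. The effect can be smaller for QALYs, and the cost-QALY slope could be too low or too high. In the setting simulated, the stated rule did worse than not imputing at all.

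The drop-out range, the coefficients of 0.40 and the complete omission of the covariate are assumptions, not protocol figures. Partial omission, or an omitted covariate correlated with an included one, would change the size.

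**What to change.** Replace the imputation sentence in section 15.9 with one stating that:

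- the chained equations include every variable in the analysis models and every AIC candidate: site, demographics, recency of assault, all baseline scales, care pathway and service use, and 6-month costs, CORE and ReQoL;
- baseline predictors of missingness are added as auxiliary variables, and are not the criterion for entry;
- a complete-case analysis is reported as a sensitivity analysis.

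The cost is a change of wording and a little more analysis. All the variables are already to be collected, and the design, sample size and follow-up are unaffected.

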### **15.10. Data Handling & Management**

The information provided by participants will be confidential, and, in accordance with the Data Protection Act (2018) and GDPR (2018), any personal data (identifiable details) will be stored separately from the research data (i.e. answers given during on the questionnaire). Research data will be pseudonymised using a study number. The only exception to this confidentiality is if the research team have concerns about current or future risk of serious harm to the participant or to anybody else. Similarly, confidentiality may be broken if participants disclose details of intention to commit a crime or

if participants share details of a crime for which they have not been convicted. If this happens, the research team will follow standard operating procedures (SOPs) which will cover things like informing the participants GP or other relevant services (on a need to know basis only). Researchers will always try and discuss this with participants first where possible.

As well as being used to support the current research, data that has been pseudonymised and/or anonymized (i.e. questionnaire data that has had your identifiable information removed and been given a study number) may also be used to support relevant future research and/or training and may be shared anonymously with other researchers (subject to relevant research governance processes such as confidentiality and data access agreements). Anonymised data may also be made available indefinitely on database repositories for publication purposes to increase transparency of research process.

Identifiable, personal data will be kept for 2 years and then securely destroyed. If participants consent their identifiable information will be used to let them know about relevant future research opportunities (including WP4). Participants do not need to consent to further contact in order to participate in WP3. Monitors and auditors, the sponsor and regulatory inspectors may require access to personal data to verify or cross check data. They will be bound by the same confidentiality as the researchers on the study.

Participant's rights to access, change, or move their information are limited. If participants withdraw from the study or lose capacity to consent, we will keep their information that we have already obtained. To safeguard their rights, we will use the minimum personally-identifiable information possible. More about University of Leeds's privacy notice can be found here:

<https://dataprotection.leeds.ac.uk/wp-content/uploads/sites/48/2019/02/Research-Privacy-Notice.pdf>

A Data Management Plan [MiMoS\_23240\_Data Management Plan\_v1\_16.08.2019] has been developed for WP 3, 4 and 5 to compliment this protocol.

